To characterise the safety and tolerability of anifrolumab	Adverse events (AEs) (including AEs of special interest [AESIs]), vital signs, physical examination, baseline and End of Treatment 12-lead electrocardiograms (ECG), and clinical laboratory tests (haematology, clinical chemistry, urinalysis), Columbia-Suicide Severity Rating Scale (C-SSRS), Personal Health Questionnaire Depression Scale-8, extra-renal flares using Systemic Lupus Erythematosus Disease Activity Index 2000 (SLEDAI 2K) based Flare Assessment Instrument

Exploratory Objective:	Outcome Measures:
To evaluate the effect of anifrolumab plus SOC ^a compared with placebo plus SOC ^a on:	
CCI [Redacted]	[Redacted]
CCI [Redacted]	[Redacted]
CCI [Redacted]	[Redacted]

Exploratory Objective:	Outcome Measures:

Proportion of subjects achieving alternative CRR (aCRR) at Week 52 (and Week 104)
 
The difference between the CRR and the aCRR is the addition of a criterion regarding “inactive urine sediment”
	
aCRR is defined as meeting all of the following:
 
 • eGFR is 
 ≥60 mL/min/1.73 m² or no confirmed decrease of eGFR from baseline of ≥20% • 24-hour UPCR ≤0.7 mg/mg • Inactive urine sediment (defined as <10 red blood cells [RBC]/hpf) • No discontinuation of IP or use of restricted medication^b beyond the protocol-allowed threshold before assessment 
eGFR is based on MDRD formula

CCI [REDACTED]
	
[REDACTED]
 
[REDACTED]
 
[REDACTED]
 
[REDACTED]
 
[REDACTED]
 
[REDACTED]
 
[REDACTED]
 
[REDACTED]

Exploratory Objective:	Outcome Measures:
Proportion of subjects meeting Graded aCRR at Week 52 (and Week 104)	
Graded aCRR is defined as meeting both the 24-hour UPCR and eGFR criteria:
 
 • A decrease in 24-hour UPCR: 
 - For subjects with baseline UPCR >3 mg/mg: UPCR ≤1 mg/mg - For subjects with baseline UPCR ≤3 mg/mg: UPCR ≤0.7 mg/mg • eGFR: 
 ≥60 mL/min/1.73 m² or no confirmed decrease of eGFR from baseline of ≥20% • Inactive urine sediment defined as <10 RBC/hpf • No discontinuation of IP or use of restricted medication^b beyond the protocol-allowed threshold before assessment
Proportion of subjects able to achieve sustained reduction in oral corticosteroids (OCS) dose at Week 52 or Week 104	
Sustained reduction of OCS dose:
 
 • Week 52: Prednisone-equivalent dose ≤7.5 mg/day by Week 24 and not exceeding this dose through Week 52 • Week 104: Prednisone-equivalent dose ≤5.0 mg/day by Week 80 and not exceeding this dose through Week 104 
and
 
 • No discontinuation of IP or use of restricted medication^b beyond the protocol-allowed threshold before assessment
Proportion of subjects achieving CRR at Week 52 or Week 104 and achieving sustained reduction of OCS dose	CRR (see definition of CRR above) Sustained reduction of OCS dose (see definition above)
CCI [REDACTED]	[REDACTED]

Exploratory Objective:	Outcome Measures:
CCI [REDACTED]	[REDACTED]
CCI [REDACTED]	[REDACTED]

Exploratory Objective:	Outcome Measures:
CCI [Redacted]	[Redacted]
CCI [Redacted]	[Redacted]
Mean change in scores for overall disease activity from baseline to Week 52 (and to Week 104)	SLEDAI-2K
Mean change in score measures of non-renal disease activity from baseline to Week 52 (and to Week 104)	Non-renal components of SLEDAI-2K
Mean change in scores for overall disease activity from baseline to Week 52 (and to Week 104)	Physician’s Global Assessment (PGA)

Exploratory Objective:	Outcome Measures:
Mean change in the Systemic Lupus International Collaborating Clinics/American College of Rheumatology (SLICC/ACR) Damage Index (SDI) score from baseline to Week 52 (and to Week 104)	SDI
Mean change in scores for patient-reported health status from baseline to Week 52 (and to Week 104)	Patient Global Assessment (PtGA)
To evaluate the immunogenicity of anifrolumab, pharmacokinetics (PK), pharmacodynamics (the PK and immunogenicity results will be reported in the clinical study report)	Anti-drug antibodies (ADA), anifrolumab concentration and PK parameters, 21 gene type I IFN gene signature
To evaluate the pharmacokinetics of mycophenolic acid (MPA)	MPA concentration and PK parameters (if applicable)
Mean change in lupus serology from baseline to Week 52 (and to Week 104)	Anti-dsDNA antibodies, C3 and C4 complement levels
CCI [REDACTED]	[REDACTED]

- ^a Required SOC is described in Section 7.7.3.
- ^b Allowed medication is described in Section 7.7.
- ^c Note: Spot UPCR will be used instead of 24-hour UPCR for the PRR and CRR classification, when evaluating time to renal response modified to include OCS tapering requirement as well as for the PRR and CRR classification for flare assessment.

Target subject population

The study will be performed in adult subjects, 18 to 70 years of age with documented active proliferative LN.

Duration of treatment

The overall study duration is approximately 116 weeks. The total treatment period is approximately 100 weeks (26 doses administered every 4 weeks):

- **52 week double-blind treatment period:** IP will be administered every 4 weeks from Week 0 to Week 48 for a total of 13 doses.
- **Second year extension period:** IP will be administered every 4 weeks from Week 52 to Week 100 for a total of 13 doses plus SOC.

Investigational product, dosage and mode of administration

Approximately 150 subjects will be randomised in a 1:1:1 ratio to receive one of the two IV anifrolumab dosing regimens or placebo, as follows:

- **Basic Regimen:** Anifrolumab 300 mg IV Q4W (13 doses) plus SOC or
- **Intensified Regimen:** Anifrolumab 900 mg IV Q4W for the first 3 doses followed by 300 mg IV Q4W for an additional 10 doses plus SOC or
- **Placebo:** IV Q4W plus SOC

Subjects eligible for the second year extension will continue to receive blinded IP (in the treatment arm they were randomised to on Day 1) for another 13 doses plus SOC.

Criteria for discontinuing investigational product for worsening of LN or SLE:

At any time:

- $>30\%$ decrease in eGFR compared to baseline due to LN and eGFR <60 mL/min/1.73 m² (on two independent samples) or
- Increase in renal or extra-renal lupus activity requiring prohibited systemic immunosuppressive treatment (eg, cyclophosphamide, rituximab, belimumab)
- Receipt of >1 methylprednisolone pulse after the day of randomisation
- Receipt of any methylprednisolone pulse after Week 8
- The IP will be discontinued if MMF is discontinued and another immunosuppressant is initiated

At Week 12 and Week 24:

- eGFR $<75\%$ of baseline and <60 mL/min/1.73 m² (on two independent samples) or
- Nephrotic range UPCR (confirmed by a second measurement at least two weeks after the first measurement):
 - Subjects with 24-hour UPCR ≤ 3 mg/mg at baseline will be withdrawn if 24-hour UPCR increases by $>50\%$ from baseline to >3.5 mg/mg
 - Subjects with 24-hour UPCR >3 mg/mg at baseline will be withdrawn if 24-hour UPCR at Week 24 >3.5 mg/mg and there is $<60\%$ improvement from baseline or

- Inability to adhere to corticosteroids requirements:
 - Inability to reduce OCS to ≤ 15 mg/day prednisone-equivalent at Week 12
 - Inability to reduce OCS to < 15 mg/day by Week 24

Subjects who exceed the maximum daily OCS dose at the Week 12 or Week 24 visits may continue to receive IP if the current dose is part of a temporary increase in OCS dose (eg, protocol-allowed burst and taper). Subjects who cannot be returned to their pre-increase dose within 14 days from the start of increase will have their IP discontinued at the next visit.

Subjects who discontinue the IP before Week 48 will be followed until Week 52 (or for a minimum of 12 weeks after last dose of IP for subjects for whom IP was discontinued within 12 weeks of Week 52).

Criteria for discontinuing investigational product at Week 52:

Subjects not meeting the criteria to continue in the second year extension period will not receive any IP at Week 52 and will complete the study after completing the required follow-up visits.

Subjects meeting the following criteria may continue to receive blinded IP between Weeks 52 and 100.

- (i) Meeting all of the following criteria based on the renal portion of the PRR definition:
 - eGFR is:
 - ≥ 60 mL/min/1.73 m² or no confirmed decrease of eGFR from baseline of $\geq 20\%$
 - Improvement in 24-hour UPCR:
 - For subjects with a baseline UPCR ≤ 3 mg/mg: < 1.0 mg/mg
 - For subjects with a baseline UPCR > 3 mg/mg: $> 50\%$ improvement from baseline and ≤ 3.0 mg/mg

Renal discontinuation criteria must be confirmed in two separate samples. The second UPCR measurement should be at least 1 week after the first measurement.

- (ii) No discontinuation of IP
- (iii) Negative human immunodeficiency virus (HIV) test after signing the Main ICF

The study Medical Monitor/Designee will confirm eligibility criteria based on electronic data capture (EDC) system, and from the central laboratory.

Criteria for discontinuing investigational product at Week 52, Week 56 or Week 60:

- Failure to obtain pap smear after Week 48 with result available at Week 60 at latest
- Pap smear result not meeting the eligibility criteria (see [Appendix K](#)) at Week 52, 56, or 60 of a Pap smear obtained after Week 48
- Failure to obtain Week 52 QuantiFERON test result by Week 56

Criteria for discontinuing investigational product at Week 60 and later:

- OCS >7.5 mg/day (except one OCS burst and taper)
- MMF >2 gm/day or >Week 52 dose, whichever is lower

Subjects who discontinue the IP during the second year extension period will be followed until Week 104 (or for a minimum of 12 weeks after last dose of IP for subjects for whom IP was discontinued within 12 weeks of Week 104).

Statistical methods

The primary estimand is evaluating the efficacy on disease activity of anifrolumab relative to placebo in subjects with active proliferative LN. This is measured by the relative difference in change from baseline to Week 52 in 24-hour UPCR. The full analysis set, defined as subjects who are randomised and received at least 1 dose of IP (modified Intention-To-Treat) will be used, in order to reflect the effect of the initially assigned and dosed IP.

Analysis Set

The full analysis set will be used as the primary population for reporting efficacy and safety data. This comprises all subjects randomised into the study who receive at least 1 dose of IP and will be analysed according to randomised treatment (modified Intention-To-Treat principle). Any major deviations from randomised treatment will be listed and considered when interpreting the safety data.

Analysis method for primary endpoint

The analysis will be performed using a mixed model repeated measures fitted to log-transformed data comparing the pooled anifrolumab group (Basic and Intensified) with the placebo group, with fixed effects for treatment group, visit, stratification factors and log-transformed 24 hour UPCR at baseline. An interaction term for visit and treatment will also be included in the model to allow the relationship to differ across treatment groups. Note that visit will be fitted as a repeated variable in the model. Model assumptions will be checked

and, if not met, appropriate data transformations may be applied or non-parametric approaches will be considered.

Analysis method for safety endpoints

All safety variables will be analysed descriptively. The safety analysis will be based on the full analysis set.

Interim analysis

One interim analysis may be conducted after approximately 50% of subjects have completed the Week 52 visit. CCI

Sample size calculations

A total of 150 subjects will be randomised in a 1:1:1 ratio to receive one of the two IV anifrolumab dosing regimens (Basic Regimen or Intensified Regimen) or placebo.

The sample size is based on the following assumptions:

- Reductions from baseline to Week 52 in 24-hour UPCR of 65% and 46% for the anifrolumab and placebo arms, respectively (ie, ratios of 24-hours UPCR from Week 52 to baseline of 0.35 and 0.54, respectively), based on data presented in Furie et al, 2014¹.
- The log-transformed 24-hour UPCR values follow a normal distribution with a standard deviation (SD) of 0.8, based on data from the anifrolumab Phase 2b study (CD1013).

Based on these assumptions, a sample size of 50 subjects per arm would result in an observed relative difference in the change from baseline to Week 52 in 24-hour UPCR of 0.65 (here expressed as the ratio, comparing anifrolumab to placebo), and a corresponding 95% confidence interval (CI) of (0.50, 0.85) comparing the pooled anifrolumab group (Basic and Intensified) with the placebo group. If the interim analysis is performed, a 0.001 two-sided alpha will be spent, and the final analysis will be based on a 2-sided alpha of 0.049 (East Version 6.4). This sample size provides approximately 86% power with a 2-sided alpha of 0.049 to reject the hypothesis of no effect (relative difference =1) for comparing the pooled anifrolumab treatment group with placebo. The minimal detectable relative difference in the change from baseline to Week 52 in 24-hour UPCR between the pooled anifrolumab treatment group versus placebo is approximately 0.76, corresponding to a reduction from baseline to Week 52 in 24-hour UPCR of 59% in the pooled anifrolumab group (ratio of 24-hour UPCR from Week 52 to baseline of 0.41).

¹ Furie R, Nicholls K, Cheng TT, Houssiau F, Burgos-Vargas R, Chen SL, et al. Efficacy and safety of abatacept in lupus nephritis: a twelve-month, randomized, double-blind study. *Arthritis Rheumatol.* 2014;66(2):379-839.

	PAGE
TITLE PAGE	1
VERSION HISTORY	2
CLINICAL STUDY PROTOCOL SYNOPSIS.....	18
TABLE OF CONTENTS.....	33
1. INTRODUCTION	48
1.1 Background and rationale for conducting this study	48
1.2 Rationale for study design, doses and control groups.....	51
1.2.1 Rationale for study design	51
1.2.2 Rationale for primary endpoint selection.....	52
1.2.3 Rationale for duration of treatment.....	53
1.2.4 Rationale for dose selection	53
1.2.5 Rationale for duration of infusion.....	54
1.2.6 Interferon test background	54
1.3 Benefit/risk and ethical assessment.....	55
1.4 Study Design	57
1.5 Study governance and oversight	63
1.5.1 Data and Safety Monitoring Board	63

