6.10 Medication Error

For the purposes of this clinical study a medication error is an unintended failure or mistake in the treatment process for an AstraZeneca study drug that either causes harm to the subject or has the potential to cause harm to the subject.

A medication error is not lack of efficacy of the drug, but rather a human or process related failure while the drug is in control of the study site staff or subject.

Medication error includes situations where an error.

- occurred
- was identified and intercepted before the subject received the drug
- did not occur, but circumstances were recognised that could have led to an error

Examples of events to be reported in clinical studies as medication errors:

- Drug name confusion
- Dispensing error eg, medication prepared incorrectly, even if it was not actually given to the subject
- Drug not administered as indicated, for example, wrong route or wrong site of administration
- Drug not taken as indicated eg, tablet dissolved in water when it should be taken as a solid tablet
- Drug not stored as instructed eg, kept in the fridge when it should be at room temperature
- Wrong subject received the medication (excluding IVRS/IWRS errors)
- Wrong drug administered to subject (excluding IVRS/IWRS errors)

Examples of events that **do not** require reporting as medication errors in clinical studies:

- Errors related to or resulting from IVRS/IWRS - including those which lead to one of the above listed events that would otherwise have been a medication error
- Subject accidentally missed drug dose(s) eg, forgot to take medication
- Accidental overdose (will be captured as an overdose)
- Subject failed to return unused medication or empty packaging
- Errors related to background and rescue medication, or standard of care medication in open-label studies, even if an AZ product

Medication errors are not regarded as AEs but AEs may occur as a consequence of the medication error.

If an medication error occurs in the course of the study, then the Principal Investigator or other site personnel informs the appropriate AstraZeneca representatives within 1 day ie, immediately but **no later than 24 hours** of when he or she becomes aware of it.

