8.3.2 Full analysis set

The full analysis set will be used as the primary population for reporting efficacy and safety data. This comprises all subjects randomised into the study who receive at least 1 dose of IP and will be analysed according to randomised treatment (mITT principle). Any major deviations from randomised treatment will be listed and considered when interpreting the safety data.

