8.3.3 Pharmacokinetic analysis set

All subjects who received anifrolumab and who had at least one quantifiable serum PK observation post first dose will be included in the PK analysis dataset. All PK summaries will be based on this analysis set.

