2.1.2 Full analysis set

The full analysis set will be used as the primary population for reporting efficacy and safety data. This comprises all subjects randomised into the study who receive at least one dose of IP and will be analysed according to randomised treatment (modified intent-to-treat [mITT] principle). Any major deviations from randomised treatment will be listed and considered when interpreting the safety data.

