4.2.6 Analysis methods for safety variables

Safety variables will be summarised by treatment group for the full analysis set.

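### Safety is tabulated by randomised arm with no set by treatment received, so a placebo subject given anifrolumab by mistake keeps later events and exposure time under placebo

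*Protocol*

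**What the plan says.** The protocol synopsis (Statistical methods, Analysis Set) and Protocol 8.3.2 define the full analysis set as all randomised subjects with at least one dose of IP. The grouping rule in the synopsis is that they "will be analysed according to randomised treatment (modified Intention-To-Treat principle"), and in 8.3.2 that they "will be analysed according to randomised treatment (mITT principle"). The synopsis adds that "The safety analysis will be based on the full analysis set".

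The SAP keeps this. Section 2.1.2 states that "The full analysis set will be used as the primary population for reporting efficacy and safety data", again by randomised treatment. Section 4.2.6 states that "Safety variables will be summarised by treatment group for the full analysis set". Section 4.2.7 puts the immunogenicity analyses on the same set unless stated otherwise, and 4.2.7.1 names it for the ADA summaries by visit.

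One sentence, in both documents, deals with subjects who received something other than their allocation: "Any major deviations from randomised treatment will be listed and considered when interpreting the safety data".

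Only two other sets exist. The all-subjects set is for disposition and screening failures. The pharmacokinetic set is defined by what was received: "All subjects who received anifrolumab and who had at least one quantifiable serum PK observation post first dose". SAP Section 6 records no change on safety populations.

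**The concern.** Grouping by randomised arm protects the efficacy comparison. The safety objective (Protocol 2.3) is different: it is to characterise anifrolumab, and that depends on what subjects were actually given.

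Under the stated rule, a placebo subject who receives an active kit remains a placebo subject in the adverse event, AESI, laboratory and ADA tables. The denominators are affected as well as the counts. SAP 3.6.1 builds event rates per 100 subject-years from each subject's exposure time, and it derives time to first herpes zoster and time at risk, all by arm. The same subject could be in the pharmacokinetic set as exposed, given a quantifiable sample, and in the safety tables as unexposed.

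With about 50 subjects in the comparator, one event is a visible share of any uncommon category. Herpes zoster reactivation is already an identified risk for this drug (Protocol 1.3), so the placebo count for such events should not contain events that followed active drug.

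**Working it through.** There is no plan figure to reproduce. The check compares the rules and then works one example.

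**Rules side by side**

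| Output | Set | Grouping |
|---|---|---|
| Efficacy | Full analysis set | Randomised arm |
| Adverse events, AESIs, laboratory, vital signs (SAP 4.2.6) | Full analysis set | Randomised arm |
| ADA (SAP 4.2.7, 4.2.7.1) | Full analysis set | Randomised arm |
| PK (Protocol 8.3.3, SAP 2.1.3) | PK set | Entry requires receipt of anifrolumab |

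No row re-tabulates safety by treatment received, either as a main or a supplementary summary.

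**Inputs for the example**

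- 50 subjects per arm, 100 pooled anifrolumab (Protocol 8.2).
- Year-one exposure for a subject with all 13 doses, from SAP 3.5.5: (337 + 28) − 1 + 1 = 365 days.
- Assumed: one placebo subject gets one active 300 mg kit at Week 24 (Day 169) and then has one event. All subjects complete year one.

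**Incidence**

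- As randomised: placebo 1/50 = 2.0%; pooled anifrolumab 0/100 = 0%.
- By treatment received from the first active dose: placebo 0/50 = 0%; pooled anifrolumab 1/101 = 1.0%. The subject is in both denominators, having spent time in each state. Had the active kit been the first dose, placebo would be 0/49.
- The difference, pooled anifrolumab minus placebo, moves from −2.0 to +1.0 percentage points.

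**Rate per 100 subject-years** (subjects with an event ÷ exposure days × 365.25 × 100, SAP 3.6.1)

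- As randomised: placebo exposure is 50 × 365 = 18,250 days, so the rate is 1/18,250 × 36,525 = 2.0. Pooled anifrolumab is 0.
- By treatment received: the subject gives 168 days to placebo and 365 − 168 = 197 days to anifrolumab. Placebo exposure is 49 × 365 + 168 = 18,053 days with no event. Pooled exposure is 100 × 365 + 197 = 36,697 days, so the rate is 1/36,697 × 36,525 = 1.0.

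Each further misattributed event in a different placebo subject adds another 2.0 points to the placebo incidence for that event. With no misdosed subject the two sets of tables are identical.

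**The case against.** The strongest reply is that the rule is explicit, the same in both documents, and comes with disclosure. Major deviations from allocation are listed and considered. Important deviations are fixed before unblinding, then listed and tabulated (SAP 2.2, 4.2.5.1). Medication errors are reported within a day (Protocol 6.10). All adverse events are listed, with key information for each subject who has an AESI, a serious event, a death or an event leading to discontinuation of IP (SAP 4.2.6.1). Safety is descriptive, so no test depends on one event. Kits are assigned by IXRS and prepared by a trained unblinded person.

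Much of this stands: a misdosed subject judged major would not be invisible. But disclosure leaves the tables unchanged. It also has gaps. The word major is not defined, SAP 2.2 classifies deviations by a different term, and the medication-error route excludes IVRS/IWRS errors.

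Four stronger readings are tempting, and the documents do not support them:

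- *Misdosing is expected here.* Protocol 6.10 does include "Wrong drug administered to subject (excluding IVRS/IWRS errors"), but in a generic list that also mentions tablets dissolved in water. It says nothing about likelihood in this trial.
- *Misdosing is probable.* If one assumes a wrong kit in 0.1% to 0.5% of assignments, two thirds of them active, then over 50 × 13 = 650 placebo doses the chance of at least one misdosed placebo subject is 1 − (1 − q × 2/3)^650, or 35% to 89%. The assumed rate has no source. The result is also the chance of a misdosed subject, not of a misattributed event.
- *The rule can only hide a risk.* That direction holds for drug-related events in placebo subjects given active drug. Background events have no consistent direction, and in the opposite error nothing moves towards placebo.
- *Anyone with any active dose should be moved wholly to anifrolumab.* That would carry earlier events and mostly placebo exposure time across, and it would not settle Basic versus Intensified.

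**Conclusion.** The point holds as a conditional defect. Both documents state a rule that gives wrong safety and ADA tables if a placebo subject receives anifrolumab, and neither plans a summary that corrects them. The listing and narrative provision makes the case visible without moving the events or the exposure time.

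The size is zero without misdosing and 2 percentage points on the placebo incidence per misattributed event at 50 per arm. The documents give no basis for saying how often this would happen, so no probability is attached. Efficacy conclusions are unaffected.

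**What to change.** Before unblinding, add to SAP 2.1 a safety analysis set: all subjects with at least one dose of IP, grouped by treatment received. Use it for SAP 4.2.6 and 4.2.7.1. Record it in SAP Section 6 as a change from the protocol, as that section already does for the OCS thresholds.

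State the rule for mixed exposure:

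- A placebo subject who received any anifrolumab counts under anifrolumab from the first active dose onward. Earlier events and exposure time stay under placebo.
- A subject randomised to anifrolumab counts under placebo only if every dose was placebo.
- Basic versus Intensified is assigned by whether any 900 mg dose was received.

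Keep the full analysis set by randomised arm for efficacy. The rule should be written before unblinding so that it cannot look chosen on the data. It is applied afterwards, when the kit contents are known.

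The cost is SAP wording, a treatment-received variable and a date of first active dose. Safety and efficacy group sizes may differ by a few subjects, and a subject misdosed part-way appears in two safety denominators, which a footnote can explain. If no misdosing occurs, the tables do not change.
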